We have employed DTI in the rat sciatic nerve to monitor nerve regrowth following novel PEG fusions (Fig. 9) (manuscript in preparation). **The data shown in figure 9 correlate with electrophysiology, histologic, and behavioral assessments of peripheral nerve recovery implying DTI may be an effective non-invasive technique to monitor nerve repair after repair.** Moreover, we have used PEG fusion in larger animal models such as the porcine model (Fig 10-manuscript in preparation) and DTI demonstrates similar radiographic information regarding axonal continuity.

[figure not shown]

FIG 9. DTI detects variations in axonal continuity. (Left) Fiber tracts (shown top-down in blue for six samples) stop at the severance site (red arrow). (Right) Extended tracts are detected following rat sciatic nerve injury, repair, and subsequent PEG fusion.

[figure not shown]

FIG 10. DTI of fixed porcine sciatic nerves harvested immediately following repair. Left panel: Control (left), suture repair (middle), and PEG (right). Green arrows indicate zone of repair. Right panel: FA at the site of injury displayed significant increases between cut repair and PEG groups.

Use of DTI to Assess Human Nerve Repair Outcomes

We have IRB approval for DTI based noninvasive assessment of nerve recovery after upper extremity surgical repair. In preliminary studies, DTI demonstrated total loss of axonal continuity (Fig. 11) and decreased FA distal to the injury site (Fig. 12) of the ulnar nerve after injury with neurotmesis and subsequent surgical repair one week post-op. Moreover, axonal continuity and FA are maintained in the adjacent non-injured median nerve. Serial assessments are planned to determine axonal outgrowth over time. This non-invasive approach is available for our clinic patients where we currently use DTI to detect changes in axonal continuity in the upper extremity of nerve injury (Figs. 11,12).

[figure not shown]

FIG 11. Demonstration of *in vivo* human DTI fiber tracking (fibers in blue) in (left) a control and (right) a patient one week after ulnar nerve injury and repair. Note the decreased mean fiber length in the injured nerve. Legend: MN = median nerve, UN = ulnar nerve.

[figure not shown]

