For Task 2, graded mixed nerve injury recovery will also be evaluated. For partial transections, a 3-D printed nerve cutting guide will allow graded transections of 25%, 50%, and 75%. Controls of 0% and 100% mixed nerve crush or cut injury will be from Task 1. Again, we will use 12 rats per group, sacrificed on 4 separate dates, for a total of 48 rats per group (= 3 graded transections * 48 = 144 total additional rats).

For Task 3, two additional groups will be added: autograft and conduit repair. Again, we will include 12 rats per group, sacrificed on 4 separate dates, for a total of 48 rats per group (= 2 different repairs * 48 = 96 additional rats).

For all Tasks, a total of 576 rats will be required.

Aim 2: Determine if DTI fiber tracking can predict recovery of peripheral nerve function in human case studies (crush or cut with repair). Pure sensory, motor, and mixed nerves will be evaluated.

Using the studies from Aim 1 as model of failed nerve recovery, human *in vivo* MRI case studies will be performed. DTI data will be collected at 1, 3, 6, and 12 months after injury and surgical repair. The first time

point was chosen to allow for inflammation to subside, which can confound DTI-based estimates of nerve regeneration (edema can result in increased diffusivities that can be incorrectly interpreted as changes in myelination and/or axonal integrity⁶³). We expect that changes due to degeneration/regeneration will be detectable via DTI at this time, as previous case studies noted detectable differences as early as 1 month^{50,51} (as well as our preliminary data in Figs. 11,12). The final time point of 12 months was chosen to allow adequate time for nerve regeneration. This will yield a ground truth assessment of the success of the repair at the end of the study. DTI results will be correlated with results from nerve conduction and EMG studies if clinically indicated acquired at the 3-, 6- and 12-months after surgery. **We hypothesize that DTI will be able to stratify patients that are recovering versus patients with failed repair at earlier times points than nerve conduction and EMG.** An outline of the study is shown in Figure 13.

[figure not shown]

FIG 13. Study design timeline following surgical repair. MRI will be performed at 1, 3, 6, and 12 months after surgery to estimate DTI parameters. NCS/EMG data will be collected for comparison at 3, 6, and 12 months.

Patient Population

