Subject recruitment: Patients will be recruited through consultations to the hand service at VUMC. Patients scheduled to receive nerve repair procedures meeting the criteria will be considered for participation. All patients must give informed consent prior to any study procedures. In the case of patients who are not competent to make a decision regarding study participation, they will be excluded from the study. A copy of the signed study consent document and authorization forms will be given to each patient. All signed consent documents will be stored in a locked cabinet in the office of the research coordinator or Principal Investigator, [name]. In an average year, the Vanderbilt Medical Group performed over 372 digital nerve repairs and an additional 50 repairs involving mixed nerve loss in the upper extremity. As a result, we anticipate reaching our target recruitment of 24 mixed injury subjects within approximately 18 months, leaving adequate time for sequence development in the early stages of the award (1st six months) and 12-month follow-up scan in the latter stages of the award (3rd year). It is rare to see a pure motor nerve injury (ulnar motor branch of the hand). These ulnar motor branch injuries will be additionally included through the duration of the study, but it is unlikely that more than 10 will be observed in a single center study.

Investigational Procedure

After inclusion criteria are met, a standard peri-operative anesthesia evaluation will be undertaken. If the patient is deemed to be of appropriate operative risk to undergo immediate operative repair, informed consent will be obtained and patients will be enrolled in the study. These determinations and obtainment of informed consent will be by research coordinator or principal investigator. It is anticipated that patients will be enrolled primarily through the emergency and trauma units. Clinical testing will occur as scheduled in Table 1. EMG/NCS will be performed after injury if clinically indicated, and at 1,3,6, and possibly 12 months after injury. These studies will be limited to focus on the injured nerve to decrease exam time and discomfort. If patients have fully recovered clinically, additional EMG's will not be performed.

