The eigenvalues/eigenvectors estimated from **D** will also be used to perform fiber tractography, which will be performed using the ExploreDTI toolbox⁷⁰. Seed regions-of-interest (ROIs) of each nerve will be drawn

in the most proximal slice to seed each fiber tract. FA threshold values and the angulation tolerances determine the limits for the automatic tracking of fibers. Previous work⁴³ has determined optimal reconstruction parameters for fiber tractography of healthy nerves (FA threshold = 0.2 and maximum angulation tolerance = 10). We will use these parameters as a starting point, noting that adjustments may need to be made in regenerating nerve. Tractography results will be quantified by estimating the mean length of fiber tracts as well as the relative number of fiber tracts that successfully reach ROIs defined in the most distal slice. During regeneration, we expect mean fiber lengths and relative tract numbers to increase.

Statistics

Statistical analyses will be performed using STATA/IC 13.1 (StataCorp, College Station, TX). In controls, tests will be performed to evaluate i) the relationship between DTI metrics and confounding variables (age, sex, and BMI), ii) the variability of DTI metrics between nerves and along nerve segments and iii) the repeatability of DTI metrics across scans and raters. In patients, tests will be performed to i) evaluate the ability of DTI to predict failed nerve recoveries at each time point (using evaluations at 12 months as the ground truth) and ii) evaluate correlations between the DTI parameters and EMG/NCS results.

We will first examine the potential confounding influence of BMI, age, and sex on each DTI parameter via multiple linear regression in controls. A Shapiro-Wilk test on the regression residuals will be used to test for normality. For the sake of this proposal, we assume normality and that parametric statistical tests are appropriate. We will employ corresponding non-parametric tests if normality is not observed. The effects of BMI, age, and sex on DTI parameters will be quantified via Pearson partial correlation coefficients. To test for variations across nerve and along nerve segments in control subjects, an ANOVA will be performed. If significant variation is observed, post hoc pair-wise comparisons will be performed using a Bonferroni multiple comparison test.

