To understand the ability of DTI parameters to provide estimates of nerve regeneration, it is important to first understand the reliability of the acquisition (interscan) and assessment (interrater) methodology. To estimate the interscan reliability, intraclass correlation coefficients (ICC) will be calculated for each DTI metric in the control scan-rescan data. To test for changes in DTI parameters across time, paired t-tests will also be performed between each timepoint. Finally, the interscan variabilities of DTI parameters will be estimated via the repeatability coefficient (RC), which is defined as 1.96 times the SD of the mean difference between scans. Analogous analyses will be performed for the inter-rater data, where nerve ROIs will be independently defined in 12 control subjects by two trained raters.

Patients will be grouped into “failed” or “successful” cohorts based upon our evaluations at 12 months. All tests below will be performed in three nerve segments of the injured nerve: i) proximal to the injury, ii) at the injury site, and iii) distal to the injury. The percent difference in DTI parameters between injured and non-injured arms will be used in all analyses to control for confounding factors (e.g., age). To evaluate the ability of DTI to predict failed nerve recoveries at each time point, we will perform two sets of test. First, significant difference between “failed” or “successful” groups will be tested (at each time point and nerve segment) via a Bonferroni multiple comparison test. Second, and ROC analysis will be performed to evaluate the diagnostic potential of each normalized DTI parameter at each time point and nerve segment. Finally, to evaluate relationships between DTI parameters and NCS/EMG data (e.g., CMAP), pairwise Pearson correlations and Bonferroni corrected significance values will be calculated.

Potential Pitfalls/Solutions

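### The failed/successful label behind the human group comparisons and ROC analyses has no stated criteria, and nothing blinds those who assign it to DTI or the scan readers to outcome

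*Combined protocol and SAP*

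**What the plan says.** Aim 2 schedules imaging and ground truth together. "DTI data will be collected at 1, 3, 6, and 12 months after injury and surgical repair", and of the 12-month point it says: "This will yield a ground truth assessment of the success of the repair at the end of the study". The Statistics section then evaluates DTI at each time point "using evaluations at 12 months as the ground truth", with patients placed in failed or successful "cohorts based upon our evaluations at 12 months". Two analyses use this grouping: the between-group tests and the ROC analyses, both by time point and nerve segment. The sample-size paragraph uses it too, expecting 14 successes and 10 failures among 24 patients.

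Table 1 puts MRI under outcome variables, beside the Medical Research Council grade, two-point discrimination, questionnaires and strength or dexterity tests. No text says which rows make up the 12-month evaluation.

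On who sees what, the background reports of DTI: "This non-invasive approach is available for our clinic patients where we currently use DTI to detect changes in axonal continuity". The DTI Analysis section has seed regions drawn on each nerve and allows tracking settings to be adjusted in regenerating nerve. The one independence step is that "nerve ROIs will be independently defined in 12 control subjects by two trained raters", which concerns controls. Blinding, masking and adjudication are not mentioned anywhere.

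**The concern.** In a study of predictive accuracy, the reference standard has to be fixed and applied without knowledge of the test, and the test has to be read without knowledge of the reference. Here both directions are open. An assessor who has seen tractography may resolve a borderline recovery in line with it. The team may settle on whichever definition of failure agrees best with the scans. A reader who knows how the patient is doing may draw a region or adjust a tracking threshold accordingly.

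Each of these makes DTI look better than it is. The affected analyses are the ones that answer Aim 2, whether DTI can predict recovery. The problem cannot be repaired once labels have been assigned with scans in view.

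**Working it through.** **1. Which analyses use the label.**

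| Human analysis | Uses the label? |
|---|---|
| Failed vs successful comparisons | Yes |
| ROC analyses | Yes |
| Power calculation (14/10 split) | Yes |
| Control regressions, ANOVA, ICC, repeatability, inter-rater | No |
| Objective to "evaluate correlations between the DTI parameters and EMG/NCS results" | No |

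**2. The plan's own figure.** Inputs from the sample-size paragraph: FA difference 10% of 0.5 = 0.05, SD 0.04, two-sided pooled t-test at 0.05, groups of 10 and 14.
- Standard error = 0.04 × √(1/10 + 1/14) = 0.04 × 0.414 = 0.0166.
- Noncentrality = 0.05 / 0.0166 = 3.02 on 22 degrees of freedom; critical value 2.074.
- Exact power = 0.823, against the stated 0.8, so the plan's figure is slightly conservative.
- The same effect corresponds to an AUC of Φ(0.05 / (0.04 × √2)) = Φ(0.884) = 0.81.

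Blinding changes none of these inputs.

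**3. Label chosen after seeing DTI (worst case).** The documents give no inter-outcome correlations, so 0.3 to 0.7 is an assumption. One DTI metric is unrelated to K correlated outcomes. For each outcome the worst 10 of 24 patients are called failed, and the smallest of the K t-test p-values is kept.

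| Candidate outcomes | False-positive rate at 0.05 (correlation 0.7 to 0.3) |
|---|---|
| 1 | 0.05 |
| 3 | 0.12-0.14 |
| 5 | 0.18-0.20 |

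These come from 4,000 runs per setting. A rerun with 40,000 gave 0.125-0.141 for 3 outcomes and 0.184-0.218 for 5, so the upper end for 5 may be nearer 0.22.

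Two qualifications come from the same rerun:
- Only results in the hypothesised direction support DTI. Counting those alone gives 0.06-0.07 with 3 outcomes and 0.09-0.11 with 5, against 0.025.
- The plan names a Bonferroni test without a family size. If it is 4 time points × 3 segments = 12, the per-test level is 0.05/12 = 0.0042. The rate becomes about 0.012-0.013 with 3 and 0.018-0.021 with 5. Absolute rates are small, but still about three to five times nominal.

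**4. Assessor settles borderline patients with DTI in view.** This is a different mechanism, also under assumptions: 20,000 runs, an uninformative metric, and DTI deciding only the patients nearest the cut-off.

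| Patients settled by DTI | False-positive rate | Mean AUC |
|---|---|---|
| 0 | 0.05 | 0.50 |
| 2 | 0.05 | 0.53 |
| 4 | 0.07 | 0.57 |
| 6 | 0.13 | 0.62 |

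The distortion is modest for two patients and material for six of 24. It applies most directly to the 12-month scan, which is contemporaneous with the label and is itself tested against it.

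**5. Electrodiagnostics as a separate anchor.** Figure 13 lists EMG/NCS at 12 months, but Investigational Procedure schedules it "at 1,3,6, and possibly 12 months after injury" and omits it in patients who have fully recovered clinically. It is therefore not a reference available for every patient.

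**The case against.** The strongest reply is that this is silence about detail and not a flawed design. Aim 2 concerns recovery of function, and the background describes true recovery as motor or sensory innervation of the hand. The patient-population section points to objective outcome assessment, and the Statistics section sets DTI against the 12-month evaluations as something distinct from it. The Aim 2 sentence on ground truth can be read as a remark about allowing enough time. On that reading the label is functional and only its criteria are unwritten.

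Much of this stands. A reader might infer that DTI will form part of its own reference standard, but no sentence says so. MRI's place in Table 1 and the wording of Aim 2 leave the possibility open and do not establish it. A reader might also infer that every human test is compromised, but step 1 shows otherwise. Nor do the documents support a claim that the comparison with EMG/NCS is biased through the label. Aim 2 hypothesises earlier stratification by DTI, but the only specified DTI-EMG/NCS analysis is a correlation that does not use the label.

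The simulation in step 3 is a fair target too: it is exhaustive post-hoc selection for one metric at an uncorrected 0.05. It does not model DTI entering the label.

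What the reply does not answer is conduct. Even a purely functional label can be shaped by an assessor who has seen the scans, and manually drawn regions with adjustable tracking settings can be shaped by a reader who knows the outcome. The plan prevents neither.

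**Conclusion.** The point holds in this form: the label behind the group comparisons, the ROC analyses and the 14/10 split is undefined, and neither its assignment nor the scan reading is protected from knowledge of the other. The exposure is to review bias in the main accuracy results of Aim 2. Incorporation of DTI into the label is possible under the text but not stated.

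The size is illustrative. It rests on the assumed correlations, on selection of the most favourable outcome for one metric, and on the planned 10/14 split. A reader might extend the table to every clinical row of Table 1. That is not supported, because grip strength and the nine-hole peg test are marked for mixed-nerve patients only. The Bonferroni step lowers the absolute error rates of the group tests. The plan states no corresponding correction for the ROC analyses, and a significance correction would not remove bias in an AUC in any case.

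This should be corrected; it does not invalidate the study or alter its sample size.

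**What to change.** - **Define the label before any patient DTI is analysed.** Waiting until the first 12-month visit is too late, because 1-, 3- and 6-month scans will already exist. Use measures already in Table 1 other than MRI, and exclude EMG/NCS. A single measure or a composite would serve, with the investigators' own cut-off, provided it is recorded at 12 months and applies to the cohort concerned.
- **Assign and lock it blind.** An existing team member who is not shown any DTI result assigns the label and locks it before it is joined to the imaging data.
- **Read scans blind.** Region-of-interest and tractography readers work on coded scans without outcome information. Tracking settings are fixed in advance. If regenerating nerve requires a change, make it on coded scans and apply it to all patients.
- **State in the Statistics section** which analyses use the label.

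The cost is protocol wording, file coding and some scheduling among existing staff. No patients, visits or tests are added, and N remains 24.

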Exclusion criteria: Patients will be excluded from enrollment if their injuries exhibit gross contamination, in circumstances where soft tissue coverage is inadequate, or when staged repair is planned. We will also exclude patients that are diabetic, have been diagnosed with a neuromuscular disease, or are undergoing chemotherapy, radiation therapy, or other treatments known to affect the growth of the neural and vascular system. We will exclude all patients currently enrolled in another investigational study or those who are unlikely to complete the normal regime of occupational therapy. For safety reasons, all pregnant women or women who are breast-feeding will also be excluded from this study along with subject with any ferromagnetic objects that cannot be removed (cardiac pacemakers, aneurysm clip, etc.), and/or a history of claustrophobia. All subjects will undergo a standardized MRI metal screening prior to each MRI scan, and signed consent will be obtained prior to all examinations.

Sample size: Previous optimization DTI studies in human median nerves reported mean (\pm SD) FA values of 0.7 ± 0.04 ⁴². We do not have human longitudinal data from which we can estimate an effect size; however, Takagi et al.²² performed ex vivo DTI in a rat injury model longitudinally and reported mean FA values of 0.5 following trauma (FA values are preserved across fixed and in vivo tissue⁶⁴). We, therefore, assume a similar mean FA value after surgery (0.5) with a SD taken from the aforementioned human optimization study (0.04) for our power analysis below. A conservative goal is to detect a 10% increase in FA from this decreased value to stratify successful from unsuccessful surgical interventions. If we test for

differences between these cohorts via a two-tailed pooled Student's t-test ($p = 0.05$), 24 patients would yield a study power of 0.8. Thus, assuming a failure rate of 40%, we will scan 24 patients, approximately 14 of which should have successful surgeries and 10 of which should have unsuccessful surgeries.

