Data Recorded	Study Entry	Postoperative Day				
		1	30	90	180	360
Demographics						
Age	X					
Sex	X					
Race	X					
Medical Comorbidities	X					
Surgical History	X					
Social History	X					
Worker's Compensation Status	X					
Occupation	X					
Concurrent Injuries	X					
Laboratory Values	X					
Rehabilitation Regimen		X	X	X	X	
Affected Limb Physical Examination	X	X	X	X	X	
Normal Limb Physical Examination	X		X	X	X	
Distance from Injury to Finger Tip	X					
Outcome Variables						
Pain Assessment	X	X	X	X	X	
Medical Research Council Classification	X	X	X	X	X	
Data Recorded	Study Entry					
Outcome Variables Continued						
Static 2-Point Discrimination	X	X	X	X	X	
Moving 2-Point Discrimination	X	X	X	X	X	
Michigan Hand Questionnaire	X	X	X	X	X	
Grip Strength	M	M	M	M	M	
Nine hole peg test		M	M	M	M	
Short Form 12	X	X	X	X	X	
Dash Questionnaire	X	X	X	X	X	
Complications		X	X	X	X	
MRI			X	X	X	

X = ALL COHORTS, M= MIXED NERVE

DTI Analysis

In each subject, we will acquire 15 diffusion-weighted (DW) volumes, each sensitized to diffusion along a different direction, along with a non-DW volume as described above. All DTI pre-processing and tensor estimations will be performed via FMRIB's Software Library (FSL)⁶⁹. All volumes will first be coregistered to the non-DW volume using a 3D affine transformation to correct for the effects of motion and eddy currents. If rotations to the data are applied, the gradient table will be rotated accordingly. Then, the diffusion tensor **D** will be calculated using a weighted linear least squares approach. Three eigenvalues and corresponding eigenvectors will be calculated from **D**, defining the diffusivities and principal direction of diffusion, respectively. From this, we will calculate the FA, MD, RD, and AD on a voxel-wise basis. As a reminder, MD represents the mean diffusivity across all directions, AD represents diffusivity parallel to the principal directions of the axons, RD represents diffusivity parallel to the principal directions of the axons, and FA quantifies the degree of diffusion anisotropy. During regeneration, we expect to observe an increase in FA and decrease in MD due an increase in the order and total number of diffusion barriers, respectively. The relative impact of RD and AD on these changes has yet to be established; however, it has been suggested that RD primarily reflects myelination, while AD primarily reflects axonal degeneration/regeneration^{22, 53}.

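### The Bonferroni comparison of failed and successful repairs has no stated family and makes no use of the dependence between DTI tests; a whole-patient max-T permutation test keeps the 5% error rate with modestly more power

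*Combined protocol and SAP*

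**What the plan says.** Under Aim 2, the hypothesis is that "DTI will be able to stratify patients that are recovering versus patients with failed repair at earlier times points than nerve conduction and EMG". On timing, "DTI data will be collected at 1, 3, 6, and 12 months after injury and surgical repair".

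The Statistics section groups patients by their 12-month evaluation and works in three segments of the injured nerve: proximal, injury site and distal. The group difference "will be tested (at each time point and nerve segment) via a Bonferroni multiple comparison test". A ROC analysis per parameter, visit and segment follows. The section names no primary metric, segment or visit, and does not say how many tests the Bonferroni family contains. The sentence lists time point and segment but not metric.

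DTI Analysis derives FA, MD, RD and AD from one tensor, plus two tractography measures. It states an expected direction: "During regeneration, we expect to observe an increase in FA and decrease in MD".

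The Sample size paragraph rests on a single FA comparison: a "two-tailed pooled Student's t-test ($p = 0.05$), 24 patients would yield a study power of 0.8".

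**The concern.** Bonferroni divides 0.05 by the number of tests and takes no account of how the tests move together. Here they should move together strongly. The four tensor metrics are functions of the same three eigenvalues, the segments lie along one nerve, and the visits are repeat scans of the same patient. With 24 patients sized for one test at 0.05, the power left for any single comparison is low, and some of it is given up without need. If the family is not fixed in advance, the threshold itself can be chosen after the data are seen.

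**Working it through.** **Inputs from the plan.** The authors "assume a similar mean FA value after surgery (0.5) with a SD taken from the aforementioned human optimization study (0.04"). For the effect, "A conservative goal is to detect a 10% increase in FA from this decreased value", which is 0.10 × 0.5 = 0.05, so d = 0.05/0.04 = 1.25. For the groups, "approximately 14 of which should have successful surgeries and 10 of which should have unsuccessful surgeries". There are 4 visits, 3 segments, 4 tensor metrics and 2 tractography measures.

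**Plan's own figure.** For a two-sided pooled t-test, the noncentrality is 1.25 × √(14 × 10/24) = 3.02 on 22 degrees of freedom. The critical value at 0.05 is 2.07, which gives power 0.82. With 14 versus 9, power is 0.797. So 24 is the smallest total that reaches 0.80 at a 60/40 split, and the plan's sample size is right for one unadjusted test.

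**Same test under Bonferroni.** Family sizes: 4 × 3 = 12 per metric; 12 × 4 = 48 with the tensor metrics; 12 × 6 = 72 with tractography.

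| Tests in family | Level | Critical t | Power, one FA test | Total N for 80% |
|---|---|---|---|---|
| 1 | 0.05 | 2.07 | 0.82 | 24 |
| 12 | 0.00417 | 3.20 | 0.45 | 42 |
| 48 | 0.00104 | 3.78 | 0.27 | 52 |
| 72 | 0.00069 | 3.94 | 0.23 | 54 |

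**Dependence.** With AD = λ1, RD = (λ2 + λ3)/2 (formula given under DTI of Completely Transected Nerves) and MD = (λ1 + λ2 + λ3)/3, it follows that MD = (AD + 2RD)/3 exactly. The plan analyses percent differences between arms. On that scale MD becomes a weighted average of the AD and RD percent differences, so the link remains. The tractography measures depend on the tensor but are not algebraic functions of these four.

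**What max-T recovers.** This was simulated with 14 versus 10 patients, 48 cells, an effect in the distal segment only, and assumed correlations of 0.6 between visits and 0.5 between segments. A visit counts as separated if any of its cells is significant. For that reason the Bonferroni figures exceed the single-test 0.27; the simulated FA SD among successes is also not exactly 0.04.

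| FA difference at months 1, 3, 6, 12 | Bonferroni-48 | Max-T, no ordering |
|---|---|---|
| 0.05 throughout | 0.46, 0.46, 0.46, 0.46 | 0.52, 0.52, 0.52, 0.52 |
| 0.02, 0.035, 0.05, 0.06 | 0.04, 0.16, 0.48, 0.71 | 0.05, 0.20, 0.53, 0.75 |

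Familywise error with no effect anywhere is 0.033 for Bonferroni and 0.048 for max-T. Over correlations of 0.3-0.6 (visits) and 0.3-0.5 (segments), the gain at a visit is about 0 to 0.07. At 0.8 and 0.7 it reaches about 0.12 (0.58 versus 0.46, constant effect, month 1).

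**What a fixed visit order adds or costs.** Order 6, 3, 1, each visit at 0.05, with max-T inside the visit:
- Effect from month 3 in two segments: month 6 is 0.71 against 0.44 for Bonferroni-48, and month 3 is 0.57 against 0.45. If Bonferroni also drops month 12 (36 cells), it gives 0.50 and 0.49.
- Constant effect in one segment: month 1 is 0.35-0.54 against 0.45-0.54.
- Separation at months 1 and 3 only: month-1 power falls from about 0.5 to about 0.03.

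**The case against.** Bonferroni is a correct procedure under any dependence, so nothing in the plan is invalid on this account, and a gain of at most 0.07 in most settings could be called a matter of preference. That Bonferroni is valid stands. The gain is modest, but it costs only a short program. It also comes with a decision that the plan needs anyway: what the family is.

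Four stronger readings are tempting, and the documents do not support them.
- *Bonferroni assumes unrelated tests.* It does not. It only makes no use of the relation.
- *All 48 tests are in the family.* The text does not say so. If the family is 12 tests per metric, the simulated familywise error across the four tensor metrics is about 0.09 to 0.14, and the problem becomes too little correction.
- *Visits should be tested from late to early because recovery builds up.* The plan gives the direction of FA and MD during regeneration, not how the gap between groups evolves. Aim 2 expects changes to be detectable already at 1 month, while Potential Pitfalls/Solutions warns of inflammation at early visits and says that in vivo sensitivity in humans is not yet assessed. A fixed order is therefore a bet.
- *The earliest significant visit shows how early DTI works.* The Aim 2 hypothesis is relative to NCS/EMG, and neither procedure makes that comparison.

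**Conclusion.** The point holds in a limited form. The family is undefined, and the chosen correction is more conservative than it needs to be. On the plan's inputs, power for one FA test is 0.45 at 12 tests and 0.27 at 48, against the 0.82 that underlies the sample size. Most of that loss comes from testing many cells and would remain under any method that controls the familywise rate. A max-T permutation test recovers about 0 to 0.07 at a visit.

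The single-test powers depend only on the plan's figures, with d = 1.25 carried over from raw FA to the percent difference between arms. The max-T gain also depends on correlations and effect patterns that the documents do not give. Ordering the visits is an option, not a correction. A month-12 difference is concurrent with the evaluation that defines the groups and should not count as prediction.

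**What to change.** In the Statistics section:
1. State the family: which metrics (with or without tractography), segments and visits it contains.
2. Replace Bonferroni in the group comparison by a step-down max-T permutation test. Permute the failed/successful label over whole patients, so that each patient's visits, segments and metrics stay together, and refer each |t| to the permutation distribution of the largest |t| over the family. With 14 versus 10 there are 24!/(14! × 10!) = 1,961,256 possible allocations, so the p-values are fine enough.
3. If the investigators want a fixed visit order, prespecify it with its reason and its cost should separation be transient.
4. Report month 12 as concurrent association. Do not present either test as evidence that DTI is earlier than NCS/EMG.
5. Restate the power at the error level that the chosen family implies.

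The cost is a paragraph of text and a short permutation program, written before DTI results are linked to 12-month outcomes. No extra patients, visits or scans are needed. The test's null hypothesis is that the two groups have the same joint distribution, so a marked difference in spread between groups should be examined alongside it.
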